8.13.3. Missing Start and Stop Dates for Adverse Events

No imputation for stop dates of TEAEs will be performed.

Missing and/or partial start dates of TEAEs will be imputed using the algorithms presented in the

8.13.4. Missing Birth Date

Incomplete birthday date will be imputed as follows. If only the day is missing (i.e., both year and month are known and valid), the day will be set to the first day of the month. Otherwise, if both the day and month are missing (i.e., year only is known and valid), the day will be set to the first day of the first month (January 1st). Imputed dates of birth will be flagged in the individual supportive subject data listings.

8.13.5. Missing Exposure End Date

Incomplete or missing exposure end date (last cycle) will be imputed assuming that subject took the full 12 days course of the study drug. If the subject discontinued treatment or died during this period (12 days since the start of the cycle) than the date used for imputation will be the date of treatment discontinuation or death. If the subject discontinued treatment and died during this period than the date used for imputation will be the earliest of these two dates (treatment discontinuation and death).

8.13.6. Partial or Missing Date of Start of Antitumor Therapy

The instructions presented in this subsection will be applied when it will be required to check if post-baseline antitumor therapy (specifically: systemic therapies, radiotherapy and cancer surgeries) was initiated prior to a response assessment.

1. Incomplete/partial date start of antitumor therapy will be imputed only if day only is missing. In this the last day of the month will be used for imputation.
2. Incomplete/partial date start of antitumor therapy will not be imputed only if month or year or both month and year are missing. In this case the patient will be considered as having received no post-baseline anti-tumor therapy.

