3.2.2. Key Secondary Efficacy Endpoints

Progression free survival (PFS) will serve as a key secondary efficacy endpoint of the study. PFS is defined as the time from the date of randomization until the date of the investigator-assessed radiological disease progression or death due to any cause. Patients who are alive with no disease progression as of the analysis cut-off date will be censored at the date of the last tumor assessment. Patients who receive non-study cancer treatment before disease progression, or patients with clinical but not radiologic evidence of progression will be censored at the date of the last radiologic evaluable tumor assessment before the non-study cancer treatment is initiated **CC**

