3.2.3.1. Overall Response Rate

The assessment of ORR will be based on Investigator review of radiologic images and following RECIST criteria (version 1.1 2009). ORR is defined as the proportion of patients with objective evidence of CR or PR. The primary assessment of ORR will be in the ITT population, restricted to patients with measurable disease (at least 1 target lesion) at Baseline.

At the analysis stage, the best overall response will be assigned for each patient as the best response recorded from all responses recorded from the start of treatment through the treatment period (excludes assessments during follow-up). If applicable, responses recorded after radiologic disease progression or initiation of non-study antitumor therapy will be excluded. A patient's best response assignment of SD needs to be maintained for at least 6 weeks from the start of treatment.

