4.5.6. Tumor Measurements

Computed tomography tumor assessments/imaging studies of the chest and abdomen (and pelvis if clinically indicated) must be performed and obtained at each time point listed below for all patients:

- Within 28 days prior to Day 1 of Cycle 1. Scans obtained prior to patient ICF may be used if the date of the scan is within 28 days of randomization.
- Every 8 weeks during study treatment
- For patients who discontinue treatment for reasons other than radiologic disease progression, every effort should be made to perform a tumor assessment prior to the start of new anticancer therapy.
- For patients who discontinued treatment for reasons other than radiologic disease progression, every 8 weeks until the patient develops radiologic progression or the start of new anticancer treatment (whichever occurs first)

On-site tumor assessments will be performed by the Investigator/local radiologist according to RECIST criteria (version 1.1, 2009). Results of these assessments including response for target and non-target lesions and appearance of new lesions will be the basis for the continuation or discontinuation of study medication. Response definitions are provided in [Section 11](#).

If the Investigator determines that a patient develops clinical progression manifested by symptomatic deterioration but not supported by radiologic evidence of progression, the patient should stop treatment. Symptoms of clinical progression must be documented in the patient's source documents. Every effort should be made to document objective progression even after discontinuation of treatment.

If a patient is withdrawn due to radiologic disease progression, additional CT scans are not required at the end of treatment.

The same method of assessment and the same technique must be used to characterize each identified and reported lesion at Baseline, throughout the study, and during the follow-up period. All patients' files and radiological assessments must be available for source verification. Results of any unscheduled evaluations should be recorded in the patient's source documents.

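### SAP 8.13.6 treats recorded antitumor therapy as never given when its start month or year is missing, which switches off the planned PFS censoring for those patients

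*SAP*

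**What the plan says.** SAP 8.13.6 applies when the analysis must establish whether post-baseline antitumor therapy (systemic treatment, radiotherapy or cancer surgery) "was initiated prior to a response assessment". It has two rules. If only the day is missing: "In this the last day of the month will be used for imputation". If the month, the year or both are missing, no date is imputed: "In this case the patient will be considered as having received no post-baseline anti-tumor therapy".

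Two endpoint definitions rely on that check.

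- **PFS (SAP 3.2.2).** "Patients who receive non-study cancer treatment before disease progression" are one of the groups whose time "will be censored at the date of the last radiologic evaluable tumor assessment before the non-study cancer treatment is initiated".
- **Best overall response, hence ORR and DCR (SAP 3.2.3.1).** The rule is that "responses recorded after radiologic disease progression or initiation of non-study antitumor therapy will be excluded". The same section takes best response only from assessments "through the treatment period (excludes assessments during follow-up").

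SAP 9.6.3 tabulates the number and type of systemic anticancer treatments begun in follow-up. When the start date is absent, it leaves only the time to start missing. SAP section 14 records that the start-date rule was added after version 1.05. It also says the PFS censoring rules were updated, but that detail is redacted.

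**The concern.** A missing date is a gap in knowledge about when therapy began. Rule 2 turns it into a statement that therapy did not occur, although the record shows that it did. SAP 3.2.2 makes receipt of non-study treatment before progression the trigger for censoring, and the date serves only to place the censoring time. Recoding the patient as untreated removes the trigger itself.

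What is at stake is the key secondary endpoint. Progressions, deaths or scans that follow another therapy can enter the PFS analysis of a patient whom the SAP's own definition would have censored earlier. The sensitivity analyses in SAP 10.4.3 that count the start of non-study therapy as an event would probably miss the same patients, so they are not a safeguard.

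**Working it through.** **Inputs.** The plan attaches no figure to this rule, and the OS design figures do not enter, so the main check is a comparison of the texts.

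**1. What rule 2 changes, case by case.**

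| Therapy with unknown month or year | Under SAP 3.2.2 or 3.2.3.1 | After rule 2 |
|---|---|---|
| Given after radiologic progression | PFS event at progression | Unchanged |
| Given in follow-up before radiologic progression, then progression or death | PFS censored at last usable scan before therapy | Later progression or death kept as an event, subject to the redacted censoring detail |
| As above, then an unscheduled scan without progression | Censored at last usable scan before therapy | Censored at the later scan |
| Given in follow-up, then a response | Not used: follow-up assessments are excluded | Unchanged |
| Given during the treatment period, then a response | Excluded | Kept |
| OS, any timing | Does not use therapy dates | Unchanged |

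**2. Known information is discarded.** Suppose the year is recorded as 2017, the month is unknown, and a scan took place in 2018. Every possible start date precedes that scan, so the order is certain. Rule 2 still treats the scan as made without prior therapy.

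**3. Consistency within the SAP.** Under SAP 8.13.2, a concomitant medication with a missing start month or year is kept and dated to the first dose. Under SAP 9.6.3, an undated systemic therapy begun in follow-up stays in the table. One patient can therefore appear as treated in that table and as untreated in the PFS derivation.

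**4. How many patients.** The documents give no count. Assume that 25–40% of the 500 patients start new therapy and that 2–5% of those records lack a month or year. Neither rate comes from the documents.

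- Low: 500 × 0.25 × 0.02 = 2.5
- High: 500 × 0.40 × 0.05 = 10

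Even under these rates this is an upper range for PFS, because it includes patients who had already progressed radiologically and for whom the date is irrelevant.

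**5. The missing-day rule.** Take the true day as uniform over a 365-day year. The delay to month-end, summed over all days, is 7 × 465 + 4 × 435 + 378 = 5,373 days for the 31-, 30- and 28-day months. The mean is 5,373/365 = 14.7 days and the maximum is 30. The imputed date is later than the true one on (365 − 12)/365 = 96.7% of days. The rule therefore leans late, but by a bounded amount. Rule 2 has no such bound.

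**The case against.** The plan limits the damage in several ways, and most of this stands.

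- **Scanning stops.** After discontinuation without radiologic progression, SAP 4.5.6 schedules scans "every 8 weeks until the patient develops radiologic progression or the start of new anticancer treatment (whichever occurs first"). There should normally be no scheduled scan after new therapy. A reader might divide the month-end delay by the 8-week interval and call the result the chance of a misplaced scan. The documents do not support that, because it assumes scanning continues after new therapy.
- **ORR and DCR.** A reader might infer that responses to another drug will be credited to the assigned arm. Follow-up assessments are excluded from best response, and Protocol 8.8.1 prohibits other anticancer therapy during study treatment. Leakage needs a deviation of the kind listed as MRD8 in SAP 9.2.2, with an incomplete date. Protocol 13.2.3.1 counts all responses after randomization, so exposure is wider under that definition.
- **Rarity.** Protocol 10.1.14 and 10.2.8 have sites collect anticancer therapies, and the initiation date at the 30-day visit, with contacts every 4 weeks. An unknown month or year should be uncommon.
- **Direction.** The rule is the same in both arms, and omitting censoring adds events as well as time. An inference that it favors TAS-102 is not supported.
- **Redaction.** The detailed PFS censoring rules are not visible. SAP 10.4.3 implies that the main analysis censors for missed visits, so some late deaths may be censored anyway.
- **Earliest-date imputation.** This is not a safe general remedy. Dosing ends on Day 12 (Protocol 9.2.1), and on-treatment scans fall at the end of recovery (Protocol Table 1). A start set to the day after the last dose, or to the first of the month, can precede the scan that showed progression and turn a true event into a censored time.

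It can also be argued that 8.13.6 is only a missing-data convention and so contradicts nothing. That does not stand for rule 2: a convention may place an unknown date, but this one denies a recorded treatment.

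**Conclusion.** The concern holds for rule 2. Followed as written, it misclassifies patients with recorded therapy and disables the PFS censoring that SAP 3.2.2 prescribes for them. For therapy given during the treatment period, it also disables the response exclusion in SAP 3.2.3.1.

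The effect is confined mainly to PFS. It arises through later progressions, deaths or unscheduled scans that are kept when they should follow a censoring time. ORR and DCR are largely protected, and OS is unaffected. The number affected is probably small; the range of 2.5 to 10 rests on assumed rates and is an upper range only. The direction of bias in the PFS hazard ratio cannot be determined from the documents.

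The month-end rule for a missing day is a trade-off rather than an error. It leans late, but the protocol asks for every effort to scan before new therapy, so when a scan and a therapy start share a month the scan probably came first. That half calls for a sensitivity analysis, not replacement.

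**What to change.** In SAP 8.13.6:

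1. Delete the provision that classes the patient as having had no post-baseline therapy, and keep the patient as treated.
2. Where month or year is missing, bound the start date by:
   - the known date parts;
   - from below, the end-of-treatment tumor assessment, or the last dose if there was no such scan;
   - from above, the first contact at which the therapy was recorded.
3. Do not place the start before a scan that led to treatment discontinuation. Apply the lower bound only when the record does not show therapy given during study treatment.
4. Where only the day is missing, month-end may stay in the main analysis. Add a PFS sensitivity analysis using the first of the month, subject to the same bounds.
5. Report the number of patients with imputed therapy dates by arm, so that a reader can see whether the rule matters.

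The cost is a few lines of SAP text and code, and a few patients censored earlier for PFS.

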8.14. Countries in EU

For the purpose of the present study the following countries will be defined as belonging to EU:

1. Belgium, Czech Republic, France, Germany, Ireland, Italy, Poland, Portugal, Romania, Spain, United Kingdom.
2. Belarus, Israel, Russian Federation, Turkey

9. GENERAL ANALYSIS

9.1. Subjects Disposition

A complete accounting of subject participation in the study will be presented according to requirements provided by ICH Guideline for Industry, 1996 (Structure and Content of Clinical Study Reports [CSR]) [15]. The purpose of this table is to track subjects from informed written consent through their exit from the study and to account for subject evaluation in major analyses of efficacy and safety, including reasons for early study termination or withdrawal.

9.2. Protocol Deviations

A set of “protocol deviations”/“major protocol deviations” is defined as a means to measure adherence to key aspects of the protocol. Summary of all major Protocol Deviations (at study entrance and during the study period) by type of deviation will be provided.

A summary of all protocol deviations (at study entrance and during the study period) by type of deviation will be provided.

A patient will be considered as having a protocol CSR reportable deviation if she/he meets at least one of the criteria presented below. These subjects will be identified based on reviews of the data prior to final unblinding of the treatment codes.

9.2.1. CSR Reportable Protocol Deviation

A CSR reportable Protocol Deviation is related to inclusion/exclusion criteria, conduct of the trial, patient management or patient assessments that impact the safety of the subjects or jeopardize the quality of the study data.

During the conduct of protocol TAS-102-302 the following categories will be used for CSR reportable Protocol Deviations:

RD1 - A subject that did not meet entry criteria

RD2 - A subject that developed withdrawal criteria but was not withdrawn

RD3 - A subject that received the wrong treatment or incorrect dose

RD4 - A subject that received an excluded medication

RD5 - Critical ICF, GCP and other Protocol Deviations

A CSR non-reportable Protocol Deviation may be important to address and document as part of site management and oversight, but is not considered reportable in the CSR.

The following categories will be used to capture non-reportable PDs.

NRD1 - SAE reporting

NRD2 - Informed consent

NRD3 - Study procedures

NRD4 - Investigational product (other than incorrect dose or wrong treatment)

Refer also to the study *Protocol Deviation Plan*, for details.

9.2.2. Major CSR Reportable Protocol Deviation

In addition, among all CSR Reportable Protocol Deviations, a set of “major protocol deviations” is defined as a means to measure adherence to key aspects of the protocol using pre-specified CCI analyses.

Study Entrance:

MRD1 - No histological confirmation of gastric adenocarcinoma including adenocarcinoma of the gastroesophageal (GE) junction

MRD2 - No metastatic disease

MRD3 - No measurable or nonmeasurable disease as defined by RECIST 1.1 criteria

MRD4 - Received fewer than 2 prior regimens (at least 1 cycle per regimen) of standard chemotherapy for advanced gastric or GE junction cancer or was not refractory to or was able to tolerate their last prior therapy. The regimens are supposed to meet the following criteria:

- a. Prior regimens must have included a fluoropyrimidine, platinum, and either a taxane-and/or irinotecan-containing regimen; patients whose tumors are HER2-neu-positive (HER2+) must have received prior anti-HER2+ therapy if available.
- b. Patients must have progressed based on imaging during or within 3 months of the last administration of their last prior regimen.
- c. Patients who have withdrawn from standard treatment due to unacceptable toxicity warranting discontinuation of treatment and precluding retreatment with the same agent prior to progression of disease will also be eligible to enter the study.
- d. Patients who have received postoperative adjuvant chemotherapy and radiotherapy, and had recurrence during or within 6 months of completion of the adjuvant chemotherapy are allowed to count the adjuvant therapy as one prior regimen for advanced disease. Patients who have received pre- and post-operative adjuvant chemotherapy, and had recurrence during or within 6 months of completion of the adjuvant chemotherapy are allowed to count the adjuvant therapy as one prior regimen only if the same regimen was administered both pre- and post-operatively.

MRD5 - Prior anticancer therapy within 3 weeks prior to study drug administration

MRD6 - Subject has previously received TAS-102

Study period:

MRD7 - Patient received incorrect treatment (i.e. randomized to one arm but received the other arm)

MRD8 - Other concurrent chemotherapy or radiotherapy administered while receiving study medication

The number of patients with CSR Reportable deviations of one or more criteria and the number of patients with major CSR reportable protocol deviations will be listed and tabulated for all patients (including screen failures) and ITT population.

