6.2. Rationale for Study and Selection of Dose

6.2.1. Unmet Medical Need

Gastric cancer is the fifth most common cancer worldwide and the third most common cause of cancer-related death (after lung and liver cancer), with an estimate of 723,073 deaths annually. Currently, patients with gastric cancer can be cured only when diagnosed with early stage disease in which a complete resection of the tumor can be achieved (gastrectomy with lymphadenectomy, with or without chemotherapy or radiation therapy). Approximately 50% of patients with gastric cancer have advanced disease at the time of diagnosis. Standard chemotherapy regimens for advanced gastric cancer include fluoropyrimidines, platinum derivatives, and taxanes, or irinotecan. Based on the results of the ToGA study, the addition of trastuzumab to chemotherapy has become standard of care, where available, for first-line treatment of patients with HER2-neu-positive (HER2+) advanced or metastatic gastric adenocarcinoma. Among patients with advanced metastatic gastric cancer who have received standard first-line therapies, the 5-year survival rate remains less than 5% and the median OS is less than 12 months. Ramucirumab, a vascular endothelial growth factor-2 (VEGFR-2)

antibody, has been shown to increase OS when administered alone⁵ or in combination with paclitaxel⁶ in patients who have progressed following first-line therapy; and was recently approved in select countries for second-line therapy of gastric cancer. However, after failure of first- and second-line therapies, there are no approved or standard 3rd line treatments.

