8. INVESTIGATIONAL PLAN

8.1. Overall Study Design

This is a multinational, double-blind, two-arm, parallel, randomized, Phase 3 study evaluating the efficacy and safety of TAS-102 plus BSC versus placebo plus BSC in patients with metastatic gastric cancer who have received at least 2 prior regimens for advanced disease. The study will be conducted under the sponsorship of Taiho Pharmaceutical Co., Ltd. for sites in Japan and Taiho Oncology, Inc. for sites in the rest of the world (ROW).

Eligible patients will be centrally randomized (2:1) to TAS-102 + BSC (experimental arm) or placebo + BSC (control arm) using a dynamic allocation method (biased coin) via an Interactive Voice/Web Response System (IXRS), stratified by:

- Region (ROW vs. Japan)
- ECOG performance status (0 vs. 1)
- Prior treatment with ramucirumab (yes vs. no)

Study medication should be started within 3 calendar days after the date of randomization and continue until a discontinuation criterion is met or until completion of the primary endpoint analysis, whichever is sooner.

TAS-102 (35 mg/m²/dose) or placebo will be administered orally BID, within 1 hour after completion of morning and evening meals, for 5 days a week with 2 days rest for 2 weeks, followed by a 14-day rest, repeated every 4 weeks.

Computed tomography (CT) scans will be performed at baseline and every 8 weeks thereafter until disease progression. On-site tumor assessments will be performed by the Investigator/local radiologist. Tumor assessments will be analyzed using Response Evaluation Criteria in Solid Tumors (RECIST) criteria (Version 1.1, 2009). If patient discontinuation is for reasons other than radiologic disease progression (ie, with intolerable side effects), patients will be followed every 8 weeks for tumor response until radiologic disease progression or initiation of new anticancer therapy (whichever occurs first).

Quality of life assessments (EORTC QLQ-C30 and QLQ-STO22) will be performed prior to start of dose administration in each cycle.

Standard safety monitoring will be performed and AEs will be graded using the NCI CTCAE Version 4.03.

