8.3.1. Inclusion Criteria

A patient must meet all of the following inclusion criteria to be eligible for enrollment in this study:

- 1. Has provided written informed consent.
- 2. Has histologically confirmed non-resectable, metastatic gastric adenocarcinoma including adenocarcinoma of the gastroesophageal (GE) junction as defined by the American Joint Committee on Cancer (AJCC) staging classification (7th ed., 2010). Documentation of histology of the tumor (primary or metastasis) will be required prior to enrollment. Gastroesophageal junction involvement must be documented by endoscopic, radiologic, surgical or pathology report.
- 3. Has previously received at least 2 prior regimens (at least 1 cycle per regimen) for advanced disease and were refractory to or unable to tolerate their last prior therapy:
 - a. Prior regimen(s) must have included a fluoropyrimidine, platinum, and either a taxane- and/or irinotecan-containing regimen; patients whose tumors are HER2-neupositive (HER2+) must have received prior anti-HER2+ therapy if available.
 - b. Patients have progressed based on imaging during or within 3 months of the last administration of their last prior regimen.
 - c. Patients who have withdrawn from their last prior regimen due to unacceptable toxicity warranting discontinuation of treatment and precluding retreatment with the same agent prior to progression of disease will also be eligible to enter the study.
 - d. Patients who have received postoperative adjuvant chemotherapy or chemoradiotherapy, and had recurrence during or within 6 months of completion of the adjuvant chemotherapy are allowed to count the adjuvant therapy as one prior regimen for advanced disease. Patients who have received pre- and post-operative adjuvant chemotherapy, and had recurrence during or within 6 months of completion of the adjuvant chemotherapy are allowed to count the adjuvant therapy as one prior regimen only if the same regimen was administered both pre- and post-operatively.
- 4. Has measureable or nonmeasurable disease as defined by RECIST 1.1 criteria.
- 5. Is able to take medications orally (ie, study drug must not be administered via a feeding tube).
- 6. Is ≥ 18 years of age (≥ 20 years for patients in Japan).

- 7. Has an ECOG performance status of 0 or 1 CCI at time of randomization.
- 8. Has adequate organ function as defined by the following criteria:

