Objectives: Primary: The primary objective of this study is to evaluate overall survival in patients with refractory metastatic gastric cancer receiving TAS-102 plus BSC or placebo plus BSC Key Secondary: The key secondary objective of this study is to evaluate progression-free survival in patients with refractory metastatic gastric cancer receiving TAS-102 plus BSC or placebo plus BSC. Other Secondary: Other secondary objectives of this study are to evaluate overall response rate, disease control rate, time to deterioration of ECOG performance and quality of life in patients with refractory metastatic gastric cancer receiving TAS-102 plus BSC or placebo plus BSC.		
Methodology: Double blind comparative study (investigational drug vs placebo)		
Number of Subjects (planned and analyzed): Approximately 500 patients will be randomized using a treatment allocation of 2:1 (TAS-102 plus BSC: placebo plus BSC). A target of 384 events (deaths) will be required for the primary analysis.		

Diagnosis and main criteria for inclusion (see protocol Section 2):

Male and female patients age 18 years or older (20 years or older for patients enrolled in Japan) with histologically confirmed, non-resectable, metastatic gastric adenocarcinoma including adenocarcinoma of the gastroesophageal junction, and an ECOG performance status of 0 or 1, who have received at least 2 prior regimens (at least 1 cycle per regimen) for advanced disease, and were refractory to or unable to tolerate their last prior therapy.

- Prior regimens must have included a fluoropyrimidine, platinum, and either a taxane- and/or irinotecan-containing regimen; patients whose tumors are known to be HER2-neu-positive (HER2+) must have received prior anti-HER2+ therapy if available.
- Patients have progressed based on imaging during or within 3 months of the last administration of their last prior regimen.
- Patients who have withdrawn from their last prior regimen due to unacceptable toxicity warranting discontinuation of treatment and precluding retreatment with the same agent prior to progression of disease will also be eligible to enter the study.

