9.6. Prior, Concomitant, and Survival Follow-up Medications and Therapies

9.6.1. Prior Anti-Cancer Therapies

Prior anti-cancer therapies will be summarized for the AT population and will include the following:

- Number of prior regimens (<2, 2, 3, 4≤)
- Prior therapies (fluoropyrimidine, platinum, taxane, irinotecan, ramucirumab, immunotherapy (PD1/PDL1) containing regimens, HER2i).
- Prior Treatment with Ramucirumab (Yes, No)
- Prior Treatment with Irinotecan (Yes, No)
- Prior Treatment with Taxane (Yes, No)
- Prior Treatment with Fluoropyrimidine (Yes, No)
- Prior Treatment with Platinum (Yes, No)
- Prior Treatment with HER2i
- Prior Treatment with Immunotherapy (PD1/PDL1) (Yes, No)
- Prior surgery (Yes, No)
- Previous gastrectomy (Yes, No)
- Prior Radiotherapy (Yes, No)

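### SAP deviation MRD4 counts only standard-chemotherapy regimens while eligibility counts any two regimens, so a narrow group of eligible patients meets a major entry deviation (minor)

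*SAP*

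**What the plan says.** Protocol 8.3.1, inclusion 3, sets the regimen count: "Has previously received at least 2 prior regimens (at least 1 cycle per regimen) for advanced disease". Sub-item 3a then sets the drug classes: "Prior regimen(s) must have included a fluoropyrimidine, platinum, and either a taxane- and/or irinotecan-containing regimen". The SAP synopsis repeats the count in the same unrestricted form, for patients "who have received at least 2 prior regimens (at least 1 cycle per regimen) for advanced disease".

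SAP 9.2.2 words the matching major deviation differently. Its first limb flags a patient who "Received fewer than 2 prior regimens (at least 1 cycle per regimen) of standard chemotherapy for advanced gastric or GE junction cancer". Its sub-items a to d then largely restate inclusion 3a to 3d.

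The SAP does not define standard chemotherapy. The nearest guide is Protocol 6.2.1: "Standard chemotherapy regimens for advanced gastric cancer include fluoropyrimidines, platinum derivatives, and taxanes, or irinotecan". The same section treats ramucirumab separately, as an antibody that "has been shown to increase OS when administered alone" or in combination with paclitaxel.

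SAP 9.2 says that meeting any one listed criterion is enough for a CSR reportable deviation. SAP 9.2.1 defines the entry category, RD1, as patients who failed the entry criteria. SAP 9.2.2 draws the major deviations from within the reportable ones, and closes by saying that both are listed and tabulated for all patients and for the ITT population.

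**The concern.** A deviation criterion should flag a patient only for departing from the protocol. MRD4 adds a condition that inclusion 3 does not contain, so a correctly enrolled patient can meet a major entry deviation.

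Non-chemotherapy prior regimens are foreseen in this trial. Prior ramucirumab is a stratification factor, and SAP 9.6.1 tabulates prior ramucirumab, PD1/PDL1 immunotherapy and HER2 inhibitors. SAP 9.6.1 also tabulates the number of prior regimens with no chemotherapy limit. The study report could therefore show the same patient with two prior regimens in one table and with fewer than two in the deviation table.

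At stake are the accuracy of the deviation tables and the make-up of the set of major deviators, which SAP 9.2.2 says is used in pre-specified analyses. The type of those analyses is blacked out.

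**Working it through.** The plan gives no figure on this point, so the check sets the two rules side by side and applies them to treatment histories.

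Let T be the number of prior regimens for advanced disease and C the number of those that are standard chemotherapy, taken as in Protocol 6.2.1.

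- Inclusion 3: T ≥ 2.
- Inclusion 3a: a fluoropyrimidine, a platinum, and a taxane and/or irinotecan all appear across the prior regimen(s). One regimen may supply them all.
- MRD4, first limb: flagged if C < 2.

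An eligible patient must have C ≥ 1, because 3a cannot be met without chemotherapy. An eligible patient is therefore flagged only when C = 1 and T − C ≥ 1, with that single chemotherapy regimen carrying every required class.

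The histories below are illustrative. All other eligibility criteria are assumed to be met.

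| | Prior regimens, in order | T | 3a met? | Eligible? | C | First limb of MRD4 |
|---|---|---|---|---|---|---|
| A | Fluoropyrimidine + platinum; taxane | 2 | Yes | Yes | 2 | Not flagged |
| B | Fluoropyrimidine + platinum + taxane; ramucirumab alone (or PD1/PDL1 immunotherapy) | 2 | Yes | Yes | 1 | **Flagged** |
| C | Fluoropyrimidine + platinum; ramucirumab alone | 2 | No | No | 1 | Flagged, and not eligible |
| D | Fluoropyrimidine + platinum; taxane + ramucirumab | 2 | Yes | Yes | 2 | Not flagged |
| E | Fluoropyrimidine + platinum; taxane; ramucirumab alone | 3 | Yes | Yes | 2 | Not flagged |

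Only history B gives a conflict: the patient satisfies inclusion 3 and 3a and still meets MRD4.

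The SAP then contradicts itself on that patient. By the nesting in 9.2.2, a major deviator must first be a reportable deviator. On entry grounds that means RD1, and a patient who meets the entry criteria is not RD1. By the rule in 9.2 that any one listed criterion suffices, the same patient is a deviator through MRD4. Two programmers could classify this patient differently, and each could cite the SAP.

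The visible text of SAP section 14, which lists changes since version 1.05, gives no reason for the narrower wording.

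**The case against.** The strongest reply has four parts.

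**The nesting protects the patient.** If major deviations sit inside reportable ones and RD1 needs a failed entry criterion, an eligible patient cannot be a major deviator. Deviations are also identified by data review before unblinding, under a Protocol Deviation Plan that is not among the documents. This stands to the extent that the flag is not certain in practice. It does not cure MRD4, because it works only by overriding what MRD4 says.

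**Inclusion 3a may call for a separate taxane or irinotecan regimen.** The sentence ends by naming such a regimen, and the SAP's restatement uses a plain plural. If a separate regimen were required, every eligible patient would have C ≥ 2 and the extra words would do no harm. But the protocol's optional plural lets one regimen supply everything, and nothing in 3a says that the classes must come from different regimens.

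**The phrase is a loose paraphrase, not a second counting rule.** That is plausible: the term is undefined, and MRD4c is similarly loose in referring to standard treatment where inclusion 3c refers to the last prior regimen. It explains the mismatch but does not remove it.

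**The consequences are easily overstated.** This part stands. A reader might make three stronger inferences, and the documents support none of them:

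- *That any eligible patient with a non-chemotherapy regimen is flagged.* Histories D and E show otherwise.
- *That deaths are lost from an efficacy analysis.* The type of analysis that uses major deviations is blacked out, and none of the populations in SAP section 7 (ITT, AT, TR) excludes deviators. There is also no figure for how many patients have history B, so any count of patients or deaths would be a guess.
- *That the treatment comparison is biased because patients who had ramucirumab alone all fall in one stratum.* They do, by definition. But the flag rests on history before randomization and is assigned before unblinding, so it gives no route to a difference between arms.

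**Conclusion.** The mismatch is real, and MRD4 is wrong as written. It counts only standard chemotherapy regimens, whereas inclusion 3 and the SAP synopsis count any regimens for advanced disease. An eligible patient with history B meets it, and the SAP's own nesting gives the opposite answer for the same patient.

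The size is small. Only patients with a single chemotherapy regimen carrying all required classes, plus at least one non-chemotherapy regimen, are affected. The number is not given and may be zero. The visible effect is confined to the deviation listings and tables; any effect on the redacted analyses cannot be judged from the text. The primary analysis of overall survival in the ITT population, its significance level and its 384-event target do not change.

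The conclusion rests on two readings: that standard chemotherapy means the cytotoxic classes named in Protocol 6.2.1, and that 3a allows one regimen to supply every class. Severity: minor.

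**What to change.** Before unblinding, delete the qualifier *of standard chemotherapy* from MRD4 and use the count in inclusion 3, so that it flags patients with fewer than two prior regimens for advanced disease, each of at least one cycle. Leave the drug classes to sub-item a, which already tests them. History C would then still be caught, through sub-item a, and history B would no longer be flagged.

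If the sponsor intends the narrower count, the SAP should define standard chemotherapy, say why MRD4 departs from inclusion 3, and state how an eligible patient who meets MRD4 fits under RD1.

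The cost is one phrase in the SAP and one programming condition. SAP 9.2 places the identification of deviators before final unblinding, so a correction made by then raises no question of being driven by the results.
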